2.4 Statistical Framework

2.4.1 Hypothesis Test

This trial is designed to establish the superiority of treatment of CPAP over usual care for the total burden of atrial fibrillation in patients with paroxysmal atrial fibrillation and concomitant moderate-severe sleep apnea.

- The primary null hypothesis is that the change in the total burden of atrial fibrillation from baseline (one month prior to randomization) to the last three months of the intervention period is equal with CPAP treatment and usual care.
- The primary alternative hypothesis is that there is a difference in change in the total burden of atrial fibrillation from baseline (one month prior to randomization) to the last three months of the intervention period between CPAP treatment and usual care.

There is only one identified primary analysis in this trial. All other efficacy analyses will be regarded as supportive or exploratory.

STATISTICAL ANALYSIS PLAN for Effect of treatment of sleep apnea in patients with paroxysmal atrial fibrillation.

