5.3.7 Subgroup Analyses

The primary outcome and the secondary outcomes AFSS AF burden (#8 in Section 5.1.4), AFSS symptom score (#9), SF-36 physical (#11), SF-36 mental (#12), ESS sum score (#13), and FOSQ sum score (#14) will be analysed in the following subgroups:

- Male vs females
- Age below median vs. age above median
- Duration of AF below median vs. duration of AF above median
- Left atrium size below median vs. left atrium size above median
- BMI below median vs. BMI above median
- Patients that use the CPAP mask for more than 4 hours a night vs. patients that use the CPAP mask for less than 4 hours a night (no change in the usual care group)
- Patients who either have a DC cardioversion or start treatment of Flecainide, Dronedaron, or Amiodarone after inclusion vs. patients who do not have a DC cardioversion or start treatment of either Flecainide, Dronedaron, or Amiodarone after inclusion.

A comparison of the effect of CPAP between the subgroups will be analysed by adding a subgroup indicator variable and an interaction term between the subgroup and treatment to the linear regression model. A significant subgroup effect will be declared if the interaction term is statistically significant at the 5% level. Within- and between subgroup effects will then be reported with mean differences and 95% confidence intervals.

6 Safety Analyses and Adverse Events

At each follow up visit all serious adverse events will be recorded in the Viedoc database with description of adverse event, with start and end date of the event. Information will be provided on the severity, causality and expectedness of the adverse event

Investigator records the maximum intensity of each AE using the levels mild, moderate, severe or life-threatening. Applicable treatment given and outcome of event will also be recorded

The summary of events will be exported from the Viedoc database. The summary of number of events will be used, rather than number of patients. Safety variables will be tabulated and presented for all patients in the safety set.

STATISTICAL ANALYSIS PLAN for Effect of treatment of sleep apnea in patients with paroxysmal atrial fibrillation.

7 Statistical Software

Stata/SE 16.0 (StataCorp LLC, College Station, TX) will be used to perform the statistical analyses, except for the analyses of the dichotomous outcome, which will be done with Matlab R2014a (The MathWorks, Inc.).

8 References

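### SAP 5.3.7 declares a subgroup effect from any single interaction at an unadjusted 5% level over about 42 tests, so a false declaration is likely even if CPAP acts alike in all subgroups

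*SAP*

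**What the plan says.** SAP 5.3.7 names the primary outcome and six secondary outcomes: AFSS AF burden, AFSS symptom score, the two SF-36 component summaries, ESS and FOSQ. The list closes with "ESS sum score (#13), and FOSQ sum score (#14) will be analysed in the following subgroups". Seven factors follow: sex, age, duration of AF, left atrium size, BMI, nightly CPAP use above or below 4 hours, and cardioversion or start of an antiarrhythmic drug after inclusion. A typical entry is "Left atrium size below median vs. left atrium size above median". The CPAP-hours entry ends "a night (no change in the usual care group", so that split exists only in the CPAP arm.

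The comparison is made by "adding a subgroup indicator variable and an interaction term between the subgroup and treatment to the linear regression model". The decision rule is: "A significant subgroup effect will be declared if the interaction term is statistically significant at the 5% level". The next sentence says that effects within and between subgroups are then given as mean differences with 95% confidence intervals.

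On the standing of these analyses, SAP 2.4.1 says: "There is only one identified primary analysis in this trial. All other efficacy analyses will be regarded as supportive or exploratory".

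**The concern.** The section does more than display estimates. It sets a yes/no rule with its own 5% threshold and applies it to each interaction separately. Nothing in 5.3.7 adjusts the threshold, ranks the factors, limits their number or cautions the reader. When many such tests are run, some will cross 5% by chance even if CPAP acts identically in every patient group.

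What is at stake is the reading of the results. In a 100-patient trial, one or two declared subgroup effects can be taken as showing who benefits from CPAP, especially if the overall result is null. The wording can also be read as giving subgroup estimates only after a significant interaction. Readers would then see the chance findings without the roughly 40 unremarkable results needed to judge them.

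**Working it through.** **The plan's own figure.** The SAP gives no error rate for the subgroup analyses. Its one reproducible design figure is the sample size in SAP 2.3. A 25% reduction from a mean of 34% is 0.25 × 34 = 8.5 percentage points. With SD 12, 80% power and two-sided 5%, the noncentral t calculation gives 33 per group, as stated. With SD 15 it gives 50 per group, or 100 in total, also as stated.

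**Number of tests.** Seven outcomes × seven factors = 49. For CPAP hours, the subgroup indicator is zero throughout the usual-care arm, so the indicator and its product with treatment are the same column. The design matrix (intercept, treatment, site, baseline, subgroup, interaction) then has rank 5 of 6, and the interaction cannot be estimated. Without that factor, 7 × 6 = 42 tests remain.

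**Expected false declarations with no effect modification.** This count does not depend on correlation between tests, provided each holds its 5% level: 42 × 0.05 = 2.1.

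**Chance of at least one, independent tests.** The formula is 1 − 0.95^k.

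| Tests | k | Chance of at least one |
|---|---|---|
| All outcomes, six factors | 42 | 88.4% |
| Primary outcome only, six factors | 6 | 26.5% |

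**Chance of at least one, correlated outcomes.** The SAP model was simulated with n = 100, 1:1 allocation, two sites and no interaction. Assumed inputs were normal errors, a baseline–outcome correlation of 0.5, four median splits, two binary factors at 30%, and little or no correlation between factors (0 or 0.1). The outcome correlation is also an assumption. There were 3,000 replicates per row, or 1,200 for the 0.8 row.

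| Outcome correlation | At least one of 42 |
|---|---|
| 0.3 | 86% |
| 0.5 | 79% |
| 0.6 | 74% |
| 0.7 | 69% |
| 0.8 | 62% |

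Separate simulations with slightly different settings gave 84–86% at 0.3, 75–76% at 0.6 and 64% at 0.8. The mean count stayed at 2.0–2.1 in every row, and the primary-outcome figure at 25–26%.

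**How large a chance finding would look.** Take AF burden with SD 12, 100 patients and an even split, so 25 patients per cell. The standard error of the interaction is 12 × √(4/25) = 4.8 points. Significance at 5% needs about 1.99 × 4.8 = 9.5 points. If a baseline correlation of 0.5 (assumed) reduces the residual SD, it needs 9.5 × √0.75 ≈ 8.3 points. Either is about as large as the 8.5-point effect for which the trial was sized.

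**Effect of adjustment.** Bonferroni over 42 tests uses 0.05/42 = 0.00119 per test and holds the chance of any false declaration to about 4.9% under independence. Power for a true 8.5-point interaction (SD 12, even split) falls from about 42% at 5% to about 6–7% at that threshold, which is also Holm's first step.

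**The case against.** The strongest reply is that the SAP has already settled the standing of these analyses: there is one primary analysis, and "All other efficacy analyses will be regarded as supportive or exploratory". A declared interaction is therefore exploratory on the plan's own terms. The SAP also specifies its factors and outcomes in advance, uses interaction tests instead of comparing separate within-subgroup P-values, and reports confidence intervals. Whether exploratory interactions need adjustment is partly convention. Treating all seven outcomes as one family is the reviewer's choice, because the SAP's rule is per interaction term. Holm over 42 tests would also make a formal declaration very unlikely even for a real interaction.

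Most of this stands. It lowers the weight of the point and argues against imposing Holm as the only remedy. It does not change how often the rule produces a declaration, and an exploratory label sits badly with a rule that declares effects.

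A reader might infer three stronger things that the documents do not support:

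- **That the rate reaches 92%.** This is 1 − 0.95^49 and counts the seven CPAP-hours tests, which cannot be estimated as written. It would apply, with 49 × 0.05 = 2.45 expected, only if that factor were recast as an estimable contrast and all tests were independent.
- **That some high figure, such as 73%, is a floor.** Any lower bound depends on assumed correlations. At 0.8 the simulated rate is already about 62%.
- **That the SAP has no multiplicity provision anywhere.** The contents list shows section 3.1 on confidence intervals and P-values, but its text was not available for this review. A general statement there cannot be excluded. What can be said is that 5.3.7 sets an explicit 5% threshold and mentions no adjustment.

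**Conclusion.** The point holds as a matter of declaration and reporting. With no effect modification, the rule in 5.3.7 is expected to yield about two false declarations per trial over 42 tests. The chance of at least one is 88% under independence and roughly 60–86% for outcome correlations between 0.8 and 0.3. Those correlations, the factor prevalences and the baseline correlation are assumptions; the count of tests and the 5% level come from the SAP. For AF burden alone the chance is about 26%.

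It would be wrong to infer that the trial's primary type I error is inflated, because the primary comparison does not pass through this rule. The figures also leave out any bias from the cardioversion/antiarrhythmic factor, which is defined by events after inclusion. The change is worth making before analysis, but it does not threaten the primary result.

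**What to change.** In SAP 5.3.7, replace the declaration sentence with wording such as:

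> All interaction estimates will be reported with 95% CIs and unadjusted P-values, whether or not significant, as exploratory. No subgroup effect will be declared on an unadjusted P-value. The number of interaction tests performed, and the number with P<0.05 expected by chance (5% of that number), will be stated.

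Expressing the chance count as 5% of the tests performed keeps the text correct whether the CPAP-hours factor is dropped (42 tests, 2.1 expected) or recast so that it can be estimated (49 tests, 2.45 expected). If the sponsor wants to keep a formal declaration, it should rest on a multiplicity-adjusted P-value, for example Holm, over a family that the SAP names. SAP 3.1 should be checked at the same time so that the two sections agree.

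The change needs no new data, only SAP wording and a complete table of interactions. The cost is that a true interaction is no longer formally declared at 5%; its estimate, confidence interval and P-value are still shown. If the Holm option is taken, the loss of power shown above should be accepted openly.

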2.1 Trial Design

The A3 study is a randomized, controlled, open-label, parallel group trial being conducted at St Olavs University Hospital, Trondheim and Oslo University Hospital, Rikshospitalet, Oslo. Patients will be randomized in a 1:1 ratio to CPAP (the intervention) or control group (50 patients in each arm). The effects of CPAP treatment on atrial fibrillation will be determined using an implanted loop recorder (Reveal LINQ™, Medtronic) that detects all arrhythmia episodes. The primary endpoint is the reduction of the total burden of atrial fibrillation after 5 months of follow-up (preablation, Phase 1 of the study). Reduction in the recurrence rate after ablation is the main secondary endpoint (Phase 2 of the study). All patients will be followed up for 12 months after ablation.

This statistical analysis plan covers Phase 1 of the study. There will be a separate statistical analysis plan for Phase 2 of the study.

Figure: Flow chart. Phase 1 of the study ends after 5 months of intervention.

STATISTICAL ANALYSIS PLAN for Effect of treatment of sleep apnea in patients with paroxysmal atrial fibrillation.

STATISTICAL ANALYSIS PLAN for Effect of treatment of sleep apnea in patients with paroxysmal atrial fibrillation.

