4.2 Withdrawal/Follow-up

The number of withdrawals will be presented.

A withdrawal is defined as participants who withdrew consent, and for which data collected cannot be used.

A lost to follow up is defined as participants who withdrew from follow-up, but allowed data collected to be used.

The status of eligible and randomised patients at trial end will be tabulated by treatment group according to

- completed intervention and assessments
- completed assessments but not intervention
- withdrew consent
- lost to follow-up

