4.3 Baseline Patient Characteristics

The following patient demographics and baseline characteristics will be summarised:

Age, years

Gender, no. (%)

BMI, kg/m²

Neck circumference, cm

Waist-to-hip ratio

LVEF, %

AHI, per hour

Obstructive apnea index, per hour

Central apnea index, per hour

Minimum SpO₂, %

SpO₂ time < 90%, %

Epworth Sleepiness score

FOSQ score

STATISTICAL ANALYSIS PLAN for Effect of treatment of sleep apnea in patients with paroxysmal atrial fibrillation.

SF-36 (Physical and Mental Component Summary)

Cardiovascular disease, no. (%)

Hypertension no. (%)

Diabetes mellitus no. (%)

Stroke/TIA no. (%)

COPD/asthma no. (%)

Previous DC cardioversion no. (%)

Beta-blocker no. (%)

ACE-I + ARB no. (%)

Calcium channel blocker no. (%)

Diuretic no. (%)

Statin no. (%)

NOACs no. (%)

Antidiabetic medication no. (%)

Flecainide no. (%)

Dronedarone no. (%)

Hb, g/dl

Creatinine, mcmol/l

NT-proBNP, ng/L

Troponin T, ng/L

Patient demographics and baseline characteristics will be summarised by randomised treatment arm and overall using descriptive statistics (N, mean, standard deviation, median, 25/75 percentiles for continuous variables, and number and percentages of patients for categorical variables. There will be no statistical analysis of treatment difference. Any clinically important imbalance between the treatment groups will be noted.

5 Analysis

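### SAP section 6 summarises safety by events and sets aside patient counts, so the proportion of patients affected in each arm will not be reported

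*SAP*

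**What the plan says.** SAP section 6 covers collection and presentation of adverse events. On collection it says "At each follow up visit all serious adverse events will be recorded in the Viedoc database", each with a description and "with start and end date of the event". It then adds: "Investigator records the maximum intensity of each AE using the levels mild, moderate, severe or life-threatening". On presentation, the summary is exported from the trial database and the unit is fixed: "The summary of number of events will be used, rather than number of patients". The next sentence names the population: "Safety variables will be tabulated and presented for all patients in the safety set".

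The trial randomises 1:1 to "CPAP (the intervention) or control group (50 patients in each arm" (SAP 2.1), and this SAP covers Phase 1 only. Elsewhere the SAP does count patients. Section 4.1 plans a CONSORT diagram that includes those who stopped the intervention, with reasons. Section 4.2 says "The status of eligible and randomised patients at trial end will be tabulated by treatment group according to" four completion or withdrawal categories.

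The protocol's Statistics section has no safety analysis. Its appendix flow chart has one row for tolerability and adverse events. The row is marked at the CPAP tolerability week, at the phone calls, and at the 3-, 6-, 9- and 12-month visits.

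**The concern.** The wording is a rule that excludes patient counts, so it cannot be read as a gap that convention would fill. A reader weighing nightly CPAP against no device wants to know how many patients had a problem. An event total does not answer that: one patient with several episodes adds as much as several patients with one each. With 50 per arm, a few such patients can drive the comparison.

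The counting window adds to this. Adverse events are collected in the tolerability week, before randomisation, when every patient uses CPAP, including those later allocated to control. They are also collected after ablation, which belongs to Phase 2. Section 6 sets neither a start nor an end for the Phase 1 count.

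**Working it through.** The plan states no safety figure, so there is nothing to reproduce. The check has two parts.

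**1. Is a patient-level count planned anywhere else?**

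- SAP 3.3 defines analysis sets and plans no safety table.
- SAP 4.1 counts patients who stopped the intervention, with reasons. This can show patients who stopped CPAP because of an event. It misses those who had an event and continued, and controls have no device to stop.
- SAP 4.2 gives status at trial end (completed, withdrew consent, lost to follow-up), not events.
- SAP 5.1 lists no safety outcome at any level.
- SAP 6 names a population for the tables, but naming a population is not a plan to count its affected members.
- The protocol's Statistics section and flow chart give a collection schedule and no analysis rule.

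None plans the number of patients with at least one AE or SAE.

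**2. What can an event total say about patients affected?**

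Inputs: n = 50 per arm (SAP 2.1). The event counts are assumed: 10 on CPAP and 5 on control.

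Formula: proportion affected = m / n, where m is the number of patients with at least one event. A total of E events (E no larger than n) fixes m only to the range 1 to E.

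| Case | CPAP: 10 events in | Control: 5 events in | CPAP affected | Control affected | Difference |
|---|---|---|---|---|---|
| A | 10 patients | 5 patients | 10/50 = 20% | 5/50 = 10% | +10 points |
| B | 5 patients | 5 patients | 5/50 = 10% | 5/50 = 10% | 0 points |

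The event summary reads 10 v 5 in both cases.

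The limits for the same totals are:

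- highest difference: 10/50 − 1/50 = 20% − 2% = +18 points
- lowest difference: 1/50 − 5/50 = 2% − 10% = −8 points

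So even the direction is not fixed. A second assumed example shows the same: 20 v 10 events is 40% v 20% if every event is in a different patient (20/50 v 10/50). It is 10% v 20% if the 20 events fall in 5 patients and the 10 in 10 patients (5/50 v 10/50).

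**The case against.** The strongest reply is that this is one sentence about presentation. Serious events are recorded individually with dates, and patients have unique identifiers (SAP 2.2), so patient counts could probably be derived at reporting. No safety test is planned, and nothing in the documents suggests that events will cluster in a few patients. All of that stands, and it limits the weight of the point. It does not remove it: as written, the SAP chooses not to use those counts, and in an open-label trial they are better fixed in advance than added once the events are known.

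A second reply is that absence cannot be fully shown. SAP 2.5 to 2.7 and 3.1 appear only in the contents list of the text available, and the abbreviations include MedDRA and SOC, which section 6 does not use. The headings of those sections do not suggest safety tables, so the claim is limited to the text available.

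Three stronger readings are tempting, and the documents do not support them.

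- **Safety tables will pool the arms.** Section 6 does not mention arms, but the SAP tabulates patient status by group, and "Patient demographics and baseline characteristics will be summarised by randomised treatment arm and overall". Silence in section 6 is missing wording, not evidence of pooling.
- **Non-serious events will not be captured.** The first sentence of section 6 mentions only serious events. However, the section grades each AE from mild upwards, and the flow chart row names both AEs and SAEs. Together these point to collection of non-serious events.
- **Events in the one-month run-in can be listed in full.** The flow chart row is blank at device implantation and at randomisation, so complete collection over that month cannot be assumed.

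**Conclusion.** The point holds. Followed as written, SAP section 6 gives event totals and no proportion of patients affected, and no other available text supplies it. The size in this trial is unknown because the documents give no AE rates. Under the assumed totals of 10 v 5 events with 50 per arm, the difference in patients affected could be +10 points or 0, and the planned summary would look the same.

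The consequence is descriptive: the safety report would be less informative than the data allow, and no efficacy conclusion changes. A reader might infer that harm from CPAP will be hidden or overstated. The documents do not show that; they show only that the planned summary could not tell the cases apart. The safety set missing from SAP 3.3 and the loose AE and SAE wording are minor notes and add no weight. This is a cheap improvement that should be made.

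**What to change.** In SAP section 6, replace the clause that sets aside patient counts with a rule to present, by randomised arm:

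- the number of events, as now planned; and
- the number and percentage of patients with at least one SAE, and with at least one AE, as recorded.

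Count from randomisation to the end of Phase 1. Report separately any events recorded in the pre-randomisation CPAP tolerability week.

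Two wording notes: define the safety set in SAP 3.3, and align the AE and SAE wording in section 6 with the flow chart row.

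The cost is SAP wording, one or two extra table rows and a short listing. Treatment, the visit schedule and the efficacy analyses are unchanged. The work assumes that the database export carries the patient identifier and, for non-serious events, a start date. Section 6 provides for dates on serious events, but the documents do not list the export fields, so this should be confirmed.
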